**Evaluation of an Incentive-based Intervention to
Improve 90-day Adherence in PAP-Naïve Patients:
Project Dahlia**

Investigational Plan

Version: **2.0**

Date: **08Jul2019**

Protocol Number: **SLP-18-08-01**

Sponsor: **ResMed Corp**
[name]
[name]
[contact]

NCT Number: **NCT03851094**

This protocol has been written in accordance with current applicable guidelines (IDE for USA) as well as all other relevant additional references, medical and legal.

The information herein is confidential and the property of ResMed Corp. It is to be used in confidence for the conduct of the clinical trial according to written agreement.

Version History

Version	Date	Notes
1.0	10Jan2019	Original Version
2.0	08Jul2019	Removed inclusion criteria for patients to have used their device less than an average of 3.5 hours of usage in the first 3 days of therapy.

Protocol Summary

Study Design:	
This is a prospective, randomized, open-label study to evaluate effectiveness of applying financial and social incentives via a smartphone-based app in helping participants achieve adherence to therapy. Randomization will consist of an allocation ratio of 2:1 (control:treatment)
 
This study will be conducted on patients with obstructive sleep apnea (OSA) who have been prescribed ResMed flow generator for positive airway pressure (PAP).
 
Participants will be randomized to one of two groups: control or intervention with Wellth app, "Restful". The study comprises up to 2 participant contacts by phone, and 3 data collection timepoints. The first contact involves consenting and enrolling the participant, providing instructions based on the arm they are randomized to, and collecting baseline data including questionnaires. Those randomized to the intervention group will have a second contact, which involves onboarding to Restful. A second administration of the questionnaires will occur at +90 days from baseline.

Intervention:	
Restful by Wellth. The intervention is use of the Restful app, which provides a small daily financial reward for achieving therapy usage goals and social support. The app will also send a daily reminder to participants to use their therapy. There is no clinical treatment intervention, as all patients included in this trial will be receiving PAP therapy per standard of care.

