3.2 STUDY DESIGN

This is a prospective, randomized, two-arm, open-label study to evaluate effectiveness of applying financial and social incentives via a smartphone-based app in helping participants achieve adherence to therapy. Randomization will include an allocation ratio of 2:1 (control:treatment).

Two 'site to participant' contacts are required during this study. These contacts can either occur at the clinical site or remotely (e.g., by telephone). During the initial contact, their interest in the study and eligibility will be confirmed, then they will be consented, asked to complete the Baseline Questionnaire, and their demographic information will be collected on case report forms (CRFs).

Participants randomized to the intervention (Group B) will be provided with information and assistance in downloading Restful to their smartphone and registering with Wellth.

At the final contact (90 days), the participant will be asked to complete an End of Study Questionnaire and the investigative staff will collect PAP therapy data for the trial period and record it on CRFs. Participants in Group B will have access to the Restful app discontinued. This completes the participant's active participation in the study.

Daily usage data from AirView will be collected and transmitted electronically from usage initiation to 90 days, and then through 180 days.

Study data will be captured on CRFs. See **Appendix A** for the **Baseline and End of Study Questionnaires**. See **Appendix B** for **Participant Instructions** related to the study procedures and the Restful app.

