3.9 DATA ANALYSIS

Baseline demographic and psychosocial factors will be summarized for each randomized group for ITT and Evaluable Populations. For continuous variables, such as age and PAP usage, the mean, standard deviation, median, and range will be presented. For categorical variables, such as gender, the number and proportion of participants in each category will be presented. Baseline demographics and psychosocial factors for the control and intervention groups will be compared with t-tests and Fisher's exact tests, as appropriate.

The primary analysis compares mean PAP usage at 90 days in the control and intervention groups using a two-way ANOVA on the ITT population. Randomization group and myAir usage (Yes/No) will be included as factors in the model. The interaction of the two factors will be considered, but will only be retained in the model if it is significant at the 5% level. Missing usage hours during a day will be imputed as 0 usage. A secondary analysis of mean PAP usage will be conducted using the Evaluable Population. A sensitivity analysis of the missing data assumption will be conducted by considering missing data as missing. In this analysis, participants with no usage data will be assumed to have a mean usage of 0 hours; other participants' mean usage will be calculated as the mean usage across nights for which there is data.

A subgroup analysis of the primary endpoint will be generated for patients who are identified as strugglers. A struggler is defined as a patient who uses their device for less than or equal to 3.5 hours/night during the first 3 days of usage. Mean PAP usage at 90 days will be compared in the control and intervention groups using a two-way ANOVA on the struggler population as described above. Descriptive statistics will also be presented for mean PAP usage, comparing strugglers and non-strugglers in control and intervention groups.

Adherence will be calculated for the ITT population from daily usage data using the Medicare definition for adherence (a patient is adherent if they use the device for more than 4 hours per night for 70% of the nights during the first 90 days of usage). Percent adherence will be compared between control and intervention groups using a logistic regression model on the ITT population. Randomization group, myAir usage, and the interaction of these two factors will be included in the model. Missing usage hours during a day will be imputed as 0 usage.

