4.2 INITIAL (ENROLLMENT) CONTACT

1. Provide patient with access to informed consent document.
2. When consent has been obtained, collect device information (device ECN, device settings, mask type), demographic, and baseline data into the electronic data capture (EDC) system.
3. Randomize participant in EDC.
 - a. Participants randomized to the Control group (Group A) will complete a set of baseline questionnaires.
 - b. Participants randomized to the Treatment group (Group B) will complete a set of baseline questionnaires and provided with instructions to download Restful to their smartphone.
 - c. Monitor both groups' PAP device usage per your standard of care.

[figure not shown]
4.3 90-DAY STUDY CONTACT

1. Both Group A and Group B will be asked to complete a set of end of study questionnaires. Restful will be 'turned off' for Group B participants.
2. Continue to monitor participants' PAP device usage per your standard of care.
3. Distribute compensation for study participation.

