5 INTERVENTION

5.1 WELLTH APP (RESTFUL)

The intervention is the use of Restful, the Wellth self-management application. There is no clinical treatment intervention, as all participants will be receiving PAP therapy per standard of care.

Restful is a smartphone-based patient engagement tool that utilizes concepts from behavioral economics to help patients improve their adherence to therapy. The intervention includes:

Financial incentive:

The incentive is \$75, and is distributed as follows: Participants unlock \$5 after completing the app introduction/onboarding, and then \$10 for successful nights on days 1, 2, 3, 5, 8, 13, and 21. Successful nights are nights where therapy is used for ≥ 4 hours. Once money is "unlocked," the reward is always visible to the participant. However, participants only receive the financial reward if they unlock all \$75 by the end of the program. In between

“pay days,” participants receive positive reinforcement messages and visual cues but no financial reward is unlocked.

Recognizing that participants are likely to struggle initially, and that there are 9 days in which participants can afford to have non-adherent nights (i.e., $30 - 21 = 9$), the participants will be granted 9 hearts in the app. These hearts represent the “misses” available to them, and they will lose a heart each non-adherent night. The program will deliver a tailored intervention message of support or encouragement after every 2 lost hearts (e.g., remind participants how close they were to a successful night).

If the participant does not meet adherence in the first 5 weeks and/or they have lost 9 hearts, then they will get a second chance. The intervention will “reboot.” Participants will not be made aware of this opportunity at the outset.

Social incentive:

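### Struggler subgroup is compared between arms, but no stated rule puts its 3-day usage window before randomisation, so the comparison is open to selection bias

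*Combined protocol and SAP*

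**What the plan says.** Section 3.9 (Data Analysis) sets the subgroup rule: "A struggler is defined as a patient who uses their device for less than or equal to 3.5 hours/night during the first 3 days". The primary usage outcome is then to be "compared in the control and intervention groups using a two-way ANOVA on the struggler population", and descriptive statistics are planned for strugglers and non-strugglers in each arm. The window is tied to device use, not to randomisation.

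On timing, the plan gives the following:

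- **Version History.** Version 2.0 is described as: "Removed inclusion criteria for patients to have used their device less than an average of 3.5 hours of usage in the first 3 days".
- **Sections 3.4, 3.5 and 4.1.** Entry needs a new diagnosis and a prescription. Past PAP use is an exclusion. No criterion mentions days of use before entry.
- **Section 4.2.** After consent, staff "collect device information (device ECN, device settings, mask type), demographic, and baseline data" and then randomise in the EDC system. Randomisation is not tied to a day of therapy.
- **Protocol Summary.** "Those randomized to the intervention group will have a second contact, which involves onboarding to Restful".
- **Section 5.1.** Money is unlocked "for successful nights on days 1, 2, 3, 5, 8, 13, and 21". A successful night is one of at least 4 h, above the 3.5 h struggler cut. The section does not say whether these are app days or therapy days.
- **Section 3.2.** "Daily usage data from AirView will be collected and transmitted electronically from usage initiation to 90 days", so the date of first use is available.

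**The concern.** A subgroup comparison keeps the protection of randomisation only if membership is fixed before treatment can influence it. While low usage in the first three days was an entry condition, membership was known at entry. Version 2.0 dropped that condition but kept an arm comparison in essentially the same group, with no replacement timing rule.

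For anyone randomised before completing three days of use, membership can depend on the arm. The app sends daily reminders and rewards nights of at least 4 h, so it could lift some participants over 3.5 h. Those left below the cut in the Restful arm would be harder to help than control strugglers. Section 1 itself cites evidence that early use predicts later adherence, so this difference would carry into 90-day usage.

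The probable result is an understated effect in strugglers, and possibly an apparent harm if the app helps only early. Low early usage was an entry criterion in version 1.0, so this subgroup carries that version's target question.

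**Working it through.** **1. The plan's own figure.** Section 3.6 gives a difference of 0.8 h, SDs of 2.5 h (control) and 2.0 h (test), 180 and 90 patients, and one-sided alpha 0.025.

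- Standard error = √(2.5²/180 + 2.0²/90) = √(0.0347 + 0.0444) = 0.281 h, so 0.8/0.281 = 2.84.
- Unequal-variance t-test power is 80.8%. The smallest 2:1 total reaching 80% is 267 (178 + 89), against 270 stated. 270/0.9 = 300.

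The sample size reproduces and is not in question. The 0.8 h is reused below as the assumed true effect.

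**2. Model for the bias.** Early (3-day) usage and 90-day usage are taken as bivariate normal.

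- From the plan: cut 3.5 h, effect 0.8 h, SD 2.5 h. The control SD is used in both arms so that the true effect is the same for everyone.
- Assumed, because the documents do not give them: mean early usage μ = 4, 4.5, 5 h; correlation ρ = 0.3, 0.5, 0.7, 0.8; early app effect e = 0, 0.4, 0.8 h; share p of windows after randomisation = 0, 0.5, 1. The floor at 0 h is ignored.

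Let a = (3.5 − μ)/2.5, b = (3.5 − μ − e)/2.5 and L(z) = φ(z)/Φ(z).

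- Strugglers, p = 1: difference = 0.8 − ρ × 2.5 × [L(b) − L(a)].
- Strugglers, 0 < p < 1: replace L(b) by the average of L(a) and L(b), weighted by (1 − p)Φ(a) and pΦ(b).
- Non-strugglers, p = 1: difference = 0.8 + ρ × 2.5 × [U(b) − U(a)], with U(z) = φ(z)/(1 − Φ(z)).

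**3. One case in full: μ = 4.5, ρ = 0.5, e = 0.8.**

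- a = −0.40, Φ(a) = 0.3446, L(a) = 0.3683/0.3446 = 1.069.
- b = −0.72, Φ(b) = 0.2358, L(b) = 0.3079/0.2358 = 1.306.
- p = 1: 0.8 − 1.25 × (1.306 − 1.069) = 0.504 h. A simulation with 4 million draws per arm gave 0.506 h.
- p = 0.5: weights 0.1723 and 0.1179 give an average of 1.165, and 0.8 − 1.25 × (1.165 − 1.069) = 0.68 h.

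**4. Range over the whole grid (true effect 0.8 h).**

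| Windows after randomisation | Early effect | Difference in strugglers | Share of effect lost |
|---|---|---|---|
| All | 0.4 h | 0.56–0.72 h | 10–30% |
| All | 0.8 h | 0.31–0.63 h | 21–62% |
| Half | 0.4 h | 0.69–0.76 h | 5–14% |
| Half | 0.8 h | 0.61–0.73 h | 9–24% |
| None, or no early effect | – | 0.80 h | 0% |

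With all windows after randomisation, the struggler share is 27–42% in control. In Restful it is 22–36% (early effect 0.4 h) or 18–30% (0.8 h). In the same setting non-strugglers show 0.62–0.74 h and 0.45–0.69 h. Both subgroups can therefore fall below the effect that holds for everyone.

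**5. Cross-check with a different model.** This simulated nightly usage between 0 and 12 h, with mean 4.5 h, between-person SD 2.2 h, night-to-night SD 2.0 h and all windows after randomisation (again assumed).

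- True effect 0.8 h throughout: about 0.30 h in strugglers against 0.78 h overall.
- Effect of 0.8 h in days 1–3 only: −0.42 h in strugglers, although the overall difference is 0.03 h. Struggler shares are 34% (control) and 23% (Restful).
- No effect: 0.0 h.

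Direction and order of magnitude agree.

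**The case against.** The strongest reply is that the problem is conditional and may be rare. Participants come from the site's database, and device settings and mask type are recorded before randomisation, so some may already be on therapy. Version 1.0 entrants had the window before entry. Onboarding is a separate contact, so the app may start after the first three therapy days. The study-flow figure and Appendix B could not be read for this review and may show the timing. All of this stands as a limit on size. It does not supply a rule: the criteria and the enrolment steps leave timing open, and the past-PAP-use exclusion, read literally, points towards entry before first use.

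The second reply is about weight. The struggler analysis is not a listed endpoint, the primary ITT analysis is untouched, and the likely bias would not create a false claim of benefit. The largest loss (62%) needs every window after randomisation, the full 0.8 h within three days and a correlation of 0.8. Sampling error is also large. In the worked case there would be about 180 × 0.345 = 62 and 90 × 0.236 = 21 strugglers, giving a standard error of √(2.5²/62 + 2.0²/21) = 0.54 h against a bias of 0.30 h. These points are fair and keep the matter below the level of the primary analysis. They do not make the comparison valid, because a wide interval centred on the wrong value is still misleading.

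Third, version 1.0 entrants supply essentially only strugglers, so a group-by-struggler interaction would partly mix struggler status with protocol version. That is correct and is taken up in the fix. It does not affect the arm comparison within strugglers.

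**Conclusion.** The concern holds. As written, section 3.9 tests the arms within a group that may be selected after randomisation on a variable the app can change. For participants whose three-day window was not complete at randomisation, the comparison is not protected by randomisation, and the descriptive struggler and non-struggler contrasts by arm are exposed in the same way.

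The actual size cannot be computed, because the documents do not give the share of such participants, the early app effect, mean early usage or its correlation with 90-day usage. Under the assumed ranges the loss runs from 5% of a true 0.8 h effect to 62%, and it is zero if the window comes first or the app has no early effect. The direction, probably against the intervention, rests on the app raising early use. This should be corrected in the SAP. Confidence is medium because the timing of enrolment relative to first use is not stated.

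**What to change.** In section 3.9:

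1. From the date of first device use and the randomisation date, classify each participant's three-day window as complete before randomisation or not. Report the counts by arm.
2. Limit the between-arm struggler ANOVA to participants with a complete window. Both the flag and struggler status are then fixed at randomisation, so the arms stay comparable.
3. Preferably test a group-by-struggler interaction in that set. Show enrolment by protocol version alongside it, because version 1.0 entrants are essentially all strugglers.
4. For everyone else, report first-three-day usage and the struggler proportion by arm as outcomes. Label any within-struggler contrast descriptive and non-causal.
5. State whether days 1, 2 and 3 in section 5.1 are app days or therapy days.

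The cost is SAP wording and one derived variable, since daily usage from first use and randomisation in the EDC system are already part of the plan. No sample-size figure changes. The drawback is a smaller struggler subgroup, possibly very small if most participants start therapy after randomisation. In that case the trial cannot answer the struggler question by a randomised comparison, and the report should say so. If every window proves to precede randomisation, the analysis is unchanged and its validity is documented.

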3.6 SAMPLE SIZE

N= 300

A minimum total sample size of 270 patients, with 2:1 randomization (180 in Control group, 90 in Test group) is required to yield an 80% probability of detecting a difference of 0.8 hours in mean usage (160% of the minimally clinically significant difference) when the standard deviation is 2.5 and 2.0 in the Control and Test groups, respectively. The required sample size was calculated in the Two Sample T-Tests Assuming Unequal Variances Procedure using NCSS Power Analysis Statistical Software, Version 16 (PASS 16¹⁴) based on a one-sided, two sample t-test, using a significance level of 0.025.

Assuming a potential 10% drop-out rate due to study withdrawal or lost-to-follow-up, the final sample size will be 300 patients (270/0.9), equating to 200 in the Control group and 100 in the Test Group. The 2:1 randomization ratio was chosen because it is more cost-effective to enroll subjects in the control group.

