Mean change in ESS and FOSQ questionnaire scales will be compared between control and intervention groups using a mixed-effects linear model on the ITT population and a two-sample t-test on the Evaluable population. In the mixed-effects model, the response variable will be the mean questionnaire score and the model will include randomized group, visit, and a randomized group by visit interaction as fixed effects and subject as a random effect.

Baseline perceived disease severity, claustrophobia, coping skills, and health literacy will be tested as moderators of the intervention's effectiveness. Baseline scores will be regressed on the primary outcome (usage), and then in a mixed-effects model, the response variable will be usage and the model will include baseline score, randomized group, and a randomized group by baseline score interaction as fixed effects and subject as a random effect.

An exploratory analysis will examine how engagement with the study is associated with PAP usage. Engagement will be measured as app usage (number of touches). A linear regression model with PAP usage as the dependent variable and engagement as the independent variable will be fit to all ITT subjects (engagement is zero for all control subjects). An exploratory analysis will also test whether the intervention has a direct or indirect effect on the following psychosocial factors: the pros and cons of change, self-efficacy, and social support. Finally, an exploratory analysis will test whether nomination of, and the extent of engagement with, a social support person moderates the intervention effectiveness.

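### The struggler analysis has no group-by-struggler interaction, so it cannot support a claim that the app works differently in strugglers

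*Combined protocol and SAP*

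**What the plan says.** Section 3.9 plans a subgroup analysis of the primary endpoint in strugglers, meaning patients who average 3.5 hours a night or fewer over their first 3 days with the device. The arms are then compared within this group: "Mean PAP usage at 90 days will be compared in the control and intervention groups using a two-way ANOVA on the struggler population", in the same way as the primary analysis. For that analysis, "Randomization group and myAir usage (Yes/No) will be included as factors in the model", and the only interaction considered is the one between those two factors.

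For the rest of the sample the section adds: "Descriptive statistics will also be presented for mean PAP usage, comparing strugglers and non-strugglers in control and intervention groups". No group-by-struggler term appears, and no arm comparison with an interval is planned in non-strugglers. The plan gives no significance level, expected struggler share or power for this analysis.

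For perceived disease severity, claustrophobia, coping skills and health literacy, by contrast, Section 3.9 specifies a model with "a randomized group by baseline score interaction as fixed effects".

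**The concern.** Two questions can be asked about strugglers. One is how large the effect is among them; the planned ANOVA addresses that. The other is whether the effect differs from that in other patients; this needs a contrast of two arm differences with its standard error, and the plan does not provide one. Because strugglers and non-strugglers are to be laid side by side by arm, readers will ask the second question. They would then have one p-value from a subset, the ITT result and a table of means.

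The practical risk is that a non-significant struggler result is set against a significant ITT result and read as the app failing in strugglers, when the subset is simply smaller.

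**Working it through.** **Inputs.** Section 3.6 gives a 0.8 h difference, SDs of 2.5 (control) and 2.0 (test), one-sided 0.025, 180 and 90 patients, raised to 200 and 100 for 10% drop-out. The struggler share *f* is not in the documents; I take 30–50% as an assumption. An unequal-variance t-test stands in for the ANOVA, ignoring myAir.

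**1. The plan's own figure.** SE = √(6.25/180 + 4/90) = 0.281 h and 0.8/0.281 = 2.84. Power by the noncentral t is 80.8%, which agrees with the plan's aim to "yield an 80% probability of detecting a difference of 0.8 hours in mean usage" "when the standard deviation is 2.5 and 2.0 in the Control and Test groups, respectively". Then 270/0.9 = 300. With 200 and 100 patients, power is 84.7%.

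**2. Power within strugglers, same effect in everyone.** With 200*f* and 100*f* patients and the planning SDs inside each stratum, SE = √(6.25/(200*f*) + 4/(100*f*)).

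| Share *f* | Strugglers (control/test) | SE (h) | Power |
|---|---|---|---|
| 30% | 60/30 | 0.487 | 37% |
| 40% | 80/40 | 0.422 | 47% |
| 50% | 100/50 | 0.377 | 56% |

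Simulating the two stratum estimates under the same assumptions, the ITT result is significant and the struggler result is not in about 49%, 39% and 30% of trials.

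**3. If early use is prognostic.** The introduction says adoption in the first 3 days predicts later adherence, so the strata probably differ in mean usage. If they differ by *D* hours and the overall SDs stay at 2.5 and 2.0, each within-stratum variance falls by *f*(1−*f*)*D*². At *f* = 50% and *D* = 3 the variances are 6.25 − 2.25 = 4.00 and 4 − 2.25 = 1.75, so SE = √(4.00/100 + 1.75/50) = 0.274 h.

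| Share *f* | Power, *D* = 2 h | Power, *D* = 3 h |
|---|---|---|
| 30% | 43% | 55% |
| 40% | 56% | 72% |
| 50% | 66% | 83% |

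**4. Precision of the interaction.** With the planning SDs in each stratum and *N* = 300, SE = √(SE² in strugglers + SE² in non-strugglers). At 50% this is √(2 × (6.25/100 + 4/50)) = 0.53 h; at 30% it is √(0.487² + 0.319²) = 0.58 h. The 95% CI is then about ±1.05 to ±1.14 h (1.96 × SE). Across shares of 20–70% and *N* of 270–300, two-sided 5% power for a 0.8 h difference in effect is 21–32%. Under step 3 the SE at *N* = 300 is 0.39–0.53 h.

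**5. Post-randomisation status.** Section 5.1 pays "for successful nights on days 1, 2, 3, 5, 8, 13, and 21", so program days 1 to 3 carry rewards. The documents do not fix whether randomisation precedes first use. If it does, the app can change who is classed as a struggler. For illustration, assume a control mean of 4.5 h, SD 2.5 in both arms for early and 90-day use, correlation 0.6–0.8 between them, and a true effect of 0.8 h in all.

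| Effect on first 3 days | Arm difference, strugglers | Arm difference, non-strugglers |
|---|---|---|
| 0 h | 0.80–0.81 h | 0.79–0.80 h |
| 0.4 h | 0.56–0.62 h | 0.64–0.68 h |
| 0.8 h | 0.32–0.45 h | 0.48–0.56 h |

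Both stratum estimates are pulled down, the struggler estimate more, so the interaction is biased as well.

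**The case against.** The best defence is that the plan never claims a differential effect here. It describes a subgroup analysis of the primary endpoint in strugglers, and where it wants effect modification it says moderators and specifies an interaction. The version history shows that low use in the first 3 days was once an entry criterion, so an estimate in that group is a reasonable aim (my inference). This stands, and it is why the within-struggler estimate should be kept.

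A reader might infer more, namely that the plan will often produce a false contrast in which one stratum is significant and the other is not. The documents do not support this. That error needs a significance test in both strata, and only strugglers are tested. The struggler test keeps its nominal error rate. The discordance in step 2 of the working misleads only if someone reads the struggler p-value against the ITT result, and the plan does not propose that inference.

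A reader might also object that the 3 classification days fall inside the 90-day average. Whether they do depends on whether the 90 days run from first use or from enrollment. If they do overlap, 3/90 = 3.3% of the outcome is affected, at most 0.03 h of a 0.8 h arm difference. That does not justify an outcome that departs from the primary endpoint.

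Finally, the 37–56% power treats struggler status as unrelated to usage. That is the pessimistic end, hence the second range.

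**Conclusion.** The concern holds in limited form. As written, the struggler analysis estimates an effect within strugglers but cannot support a statement that the app works differently there, and the plan omits a term that it uses for its baseline-score moderators. If the effect is a uniform 0.8 h, power in strugglers is about 37–56% with the planning SDs inside each stratum, or 43–83% if the strata differ by 2–3 h in mean usage. Both ranges assume 200 and 100 patients and a struggler share of 30–50%, which the documents do not give. A non-significant struggler result would therefore be weak evidence that the app fails in them. The primary analysis is unaffected.

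**What to change.** Keep the within-struggler estimate, but obtain it from one ITT model with group, myAir usage, struggler status and group-by-struggler status. Report the arm difference with 95% CI in strugglers and in non-strugglers, and the interaction estimate with its CI. Label the analysis exploratory and state that a differential effect will be claimed only from the interaction. Leave the 90-day outcome as it is.

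State as a limitation that struggler status may be a post-randomisation variable if randomisation precedes first use, and that the interaction term does not remove the resulting bias.

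The cost is a few sentences in Section 3.9 and one model; sample size, conduct and the primary analysis do not change. The downside is an imprecise interaction, which the interval will show openly.
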